### 5.2.7 Tuberculosis monitoring

Blood testing for TB will be done using the interferon-gamma release assay (IGRA) test (ie, QFT-G In-Tube Test). Evaluation of all subjects by QFT-G In-Tube Test will be performed by the central clinical laboratory according to the Study Plan (Table 2 and Table 3). Annual QFT-G testing is required for all study subjects.

Compared to culture-confirmed TB, overall, 87.6% of subjects have a positive QFT-G In-Tube Test result (Cellestis, 2005). The false negative rate in this setting appears to be over 12%. Further, the performance of the test in the setting of immunosuppressant drugs has not been evaluated. Nor has it been evaluated in individuals with medical conditions other than, or in addition to, latent TB, or TB disease. The guide also states that “Medical treatments or conditions that impair immune functions can potentially reduce IFN- $\gamma$  responses and prevent detection of a specific response to the (secretory proteins) ESAT-6 and CFP-10 (the test stimulators).”

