### **6.5 Adverse events of special interest**

An AESI is an AE of scientific and medical concern specific to understanding biologics and requires close monitoring and rapid communication by the Investigator to the Sponsor/Sponsor's delegate. An AESI may be serious or nonserious.

Adverse events of special interest in this protocol will be assessed at each visit on the CRF. The events of interest are medically significant infections (non-opportunistic serious infections and opportunistic infections including viral infection/reactivation), severe hypersensitivity reactions including anaphylaxis and immune complex disease, malignancy, *herpes zoster* with cutaneous presentation, TB (including latent TB), influenza, vasculitis (non SLE), and MACE (including stroke, myocardial infarction, or cardiovascular death). Lupus nephritis (associated with SLE; WHO or ISN/RPS Classification Class III, IV or V) is defined

not as an AESI but as a new SLEDAI AE, and diagnosis will be supported with laboratory results.

An AESI that meets 1 of the seriousness outcomes listed in Section 6.2 will be categorised as an SAE for the purposes of follow-up responsibility and safety reporting. A nonserious AESI will be categorised as an AE. For reporting of AESIs, see Section 6.8.

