#### **8.5.1 Analysis methods for safety variables**

Adverse events (AESIs and SAEs) will be summarised using incidence rates (ie, number of events divided by person-time at risk). The main treatment groups for addressing the primary objective will be “Randomised Anifrolumab 300 mg” and “Randomised Placebo”. In addition, rates will also be explored over time to describe potential changes in risks with longer exposure. All AEs will be listed.

Laboratory data for haematology and clinical chemistry will be summarised. The frequency of changes with respect to normal ranges between baseline and each post-treatment time point will be tabulated. Frequencies of clinically noteworthy values (defined in the SAP) occurring during the clinical study will also be given. Shifts from normal to abnormal between baseline and each post-baseline time point will be evaluated for urinalysis.

The rate of flares as defined by a modification of the SELENA Flare Index using the SLEDAI-2K (number of flares divided by person-time at risk) will be explored.

Other safety data will be summarised as appropriate. Further details will be provided in the SAP.

[REDACTED]

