Adverse events with missing intensity will be assumed to be severe. Events with missing relationship to study medication per the investigator will be assumed to be related. If no information about seriousness is available, the AE will be considered serious.

AEs and AEs leading to discontinuation of investigational product during treatment and follow-up will also be presented by time intervals of the first onset of the event. For this analysis, repeated events with the same preferred term will not be considered (i.e., if a subject has more than one event with the same preferred term, only the event with the earliest date of onset will be used). The following time intervals are defined for AEs during treatment and follow-up:

- Year 1:  
AEs with date of onset  $\geq$  date of first administration of investigational product and either  $<$  maximum of date of re-randomisation in LTE study and date of administration of IP in LTE study or from subjects who are not randomised into the LTE study (ie, all AEs documented in the Phase 3 feeder Studies D3461C00004 and D3461C00005 are considered AEs in Year 1). If the AE has an onset on the day of first dose of investigational product in the LTE and is recorded in the Phase 3 feeder studies, it will be considered during year 1.
- Year 2:  
AEs with date of onset  $\geq$  date of first administration of investigational product in LTE study and  $<$  date of first administration of investigational product in LTE study plus 364 days
- Year 3:  
AEs with date of onset  $\geq$  date of first administration of investigational product in LTE study plus 364 days and  $<$  date of first administration of investigational product in LTE study plus 728 days
- Year 4:  
AEs with date of onset  $\geq$  date of first administration of investigational product in LTE study plus 728 days and  $<$  date of first administration of investigational product in LTE study plus 1092 days
- After year 4:  
AEs with date of onset  $\geq$  date of first administration of investigational product in LTE study plus 1092 days

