The event rate per 100 subject years including 95% CIs will be summarised for the following categories. Summaries of AESIs will be presented by AESI category (non-opportunistic serious infections, opportunistic infections, anaphylaxis, malignancy, herpes zoster, tuberculosis, influenza, vasculitis [non SLE], and major acute cardiovascular events) and preferred term. Summaries for SAEs will be presented by MedDRA system organ class and preferred term.

- Any AESI
- Any AESI by time interval for the first onset of event – alternative event rates
- Any AE leading to discontinuation of IP by time interval for the first onset of event – alternative event rates (combined feeder & LTE study, by preferred term)
- Any AESI – alternative event rates
- Any SAE (including events with outcome = death) (during treatment and during follow-up separately. No event rate for during follow-up will be presented)
- Any SAE (including events with outcome = death) by time interval for the first onset of event – alternative event rates

The event rate per 100 subject years will be summarised by MedDRA system organ class and preferred term for the following AE categories.

- Any AE (during treatment and during follow-up separately. No event rate for during follow-up will be presented)
- Any AE by descending preferred term (during treatment, and during the LTE treatment)
- Any AE with outcome = death
- Any SAE by descending preferred term (including events with outcome = death) (during treatment, and during the LTE treatment)
- Any AE leading to discontinuation of investigational product
- Any AE by relationship to investigational product (yes, no) (multiple occurrences of an AE in 1 subjects will only be counted once as related if at least one AE is related and as not related if all occurrences are not related)
- Any AE by maximum intensity (mild, moderate, severe) (i.e., multiple occurrences of an AE in 1 subjects will only be counted once with the maximum intensity in this AE)
- Any other significant AE

The alternative event rate per 100 subject years will be summarised by MedDRA preferred term for the following AE categories.

- Any COVID-19 related AE (for the LTE Study only, only subjects remaining in the study on 11-Mar-2020 will be included)
- Any SAE prior to the COVID-19 pandemic (for the LTE Study only)
- Any SAE during the COVID-19 pandemic (for the LTE Study only, only subjects remaining in the study on 11-Mar-2020 will be included)

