#### **4.2.1.2 Vital signs**

Observed values and changes from baseline of pulse, systolic blood pressure, diastolic blood pressure, respiration rate, and body temperature, respectively, will be summarised by visit. The summary statistics presented will be minimum, 1st quartile, median, 3rd quartile, maximum, mean, and SD.

For each parameter with available criteria, the number and percentage of subjects with TELVC values will be summarised by year (using the same time windows as defined for AEs in Section 3.1.1 but Year 4 ending at Week 208 [LTE Visit 40/EDV] and not presenting the category ‘after Year 4’). Additionally, the number and percentage of subjects with at least 1 TELVC value will be presented. Percentages will be based on subjects with a measurement at baseline and at least 1 subsequent measurement of the variable (in the respective period).

For each parameter, the number and percentage of subjects with values below, within, or above the corresponding normal range will be presented as shift tables from baseline to maximum and minimum post-baseline value, respectively.

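### The AE year intervals change on the nominal annual TB test days, so a constant conversion rate shows a spurious TB excess of about 3 to 6.5 times truth in 'After year 4'

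*SAP*

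**What the plan says.** SAP 3.1.1 sorts AE onsets into Year 1 (the feeder study), Years 2 to 4 and 'After year 4'. Year 2 takes onsets strictly before "date of first administration of investigational product in LTE study plus 364 days", Year 3 those strictly before "date of first administration of investigational product in LTE study plus 728 days", and Year 4 those strictly before "date of first administration of investigational product in LTE study plus 1092 days". An onset on a cut day belongs to the next interval.

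On testing, Protocol 5.2.7 states: "Annual QFT-G testing is required for all study subjects". Protocol Tables 2 and 3 place the routine test at LTE Weeks 0, 52, 104 and 156, with a window of ±7 days at the last three. Extra tests are only for newly indeterminate results. Protocol 6.5 includes latent TB among the AESIs, and 5.2.7.2 requires a newly positive result on study to be reported as one.

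SAP 4.2.1.1 tabulates "Any AESI by time interval for the first onset of event" as alternative event rates, by AESI category including tuberculosis. Protocol 8.5.1 gives the purpose: "rates will also be explored over time to describe potential changes in risks with longer exposure".

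For vital signs, SAP 4.2.1.2 borrows the same intervals but with "Year 4 ending at Week 208 [LTE Visit 40/EDV] and not presenting the category" for later time. No such adjustment is made for AEs, AESIs or SAEs.

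**The concern.** For most subjects a latent TB conversion can be seen only at the annual test. The test that closes a year of observation sits on the day the SAP opens the next interval, so a conversion acquired during one year is often, or always, credited to the following one.

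In the middle years this largely cancels: each interval loses part of its own test and gains part of the previous one. It cannot cancel at the end. 'After year 4' receives yield from the Week 156 test, which reflects a year of conversions, but contributes only about eight weeks of time at risk, all off drug.

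The table is meant to show whether risk changes with longer exposure. For TB it could show a late rise, placed after treatment has ended, that comes only from where the cuts lie.

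**Working it through.** **Inputs.** Cut days 364, 728 and 1092 after first LTE dose (SAP 3.1.1). Tests at LTE Weeks 52, 104 and 156, ±7 days (Protocol Tables 2 and 3). Last dose at LTE Week 152. Observation to last dose + 84 days, and alternative rate = first events / time at risk within the interval (SAP 3.1.1). Annual dropout 20% or 30% (SAP 1.3). The documents give no conversion rate, no distribution of visits within the window and no onset-date rule for test-detected events, so these are assumed. The documents also state no rate by interval, so there is no planned figure to reproduce.

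**1. Cuts against test days.** 7 × 52 = 364, 7 × 104 = 728, 7 × 156 = 1092. The match is exact.

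**2. Length of 'After year 4'.** Last dose 7 × 152 = 1064. End 1064 + 84 = 1148. Days 1092 to 1148 inclusive = 57.

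**3. Closed form, constant rate, completers (1.0 = truth).**
- All tests on the nominal day: 364/57 = 6.4.
- Visits uniform over the 15 days from −7 to +7, onset at sampling: 8 of 15 possible days are on or after the cut, so 8/15 × 364/57 = 3.4. Year 2 keeps 7/15 = 0.47. Years 3 and 4 are each 7/15 + 8/15 = 1.
- Same scatter, onset 7 or more days after sampling: the earliest possible onset is −7 + 7 = 0, so every test crosses the cut and 'After year 4' is again 6.4.

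**4. Simulation.** Assumed: true rate 1.0 per 100 subject-years, perfect detection, a test at early discontinuation, LTE Day 1 sample included. Apparent rates at 0 / 20% / 30% annual dropout:

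| Assumption | Year 2 | Year 3 | Year 4 | After year 4 |
|---|---|---|---|---|
| Nominal days, onset at sampling | 0.00 / 0.10 / 0.15 | 1.02 / 1.19 / 1.28 | 1.00 / 1.19 / 1.31 | 6.4 / 6.4 / 6.4 |
| ±7 days, onset at sampling | 0.46 / 0.49 / 0.51 | 0.99 / 1.09 / 1.15 | 0.99 / 1.08 / 1.14 | 3.5 / 3.4 / 3.4 |
| ±7 days, onset 7–14 days later | 1.00 / 1.17 / 1.26 | 1.01 / 1.19 / 1.29 | 1.01 / 1.20 / 1.29 | 6.4 / 6.4 / 6.4 |

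Across repeated runs 'After year 4' was 3.3 to 3.5 in the second row and 6.3 to 6.4 in the others. Relative to Years 3 and 4 it ranges from about 3.0 (3.4/1.14) to about 6.4 (6.4/1.0).

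**5. Year 2 depends on dating.** An onset on the day of the first LTE dose that is recorded in the feeder study goes to Year 1. If onset is instead dated at a result or retest a week or two later, positives from the Day 1 sample land in Year 2 and replace what Year 2 loses at Week 52 (third row).

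**6. Sparse data.** Assuming 100 to 200 completers in a group, 'After year 4' holds 100 × 57/365.25 = 15.6 to 200 × 57/365.25 = 31.2 subject-years. A single Week 156 conversion then reads as 100/15.6 = 6.4 to 100/31.2 = 3.2 per 100 subject-years.

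**7. Consistency within the SAP.** Section 3.1.1 counts an onset up to last dose + 28 days as during treatment. For a completer on schedule that is 1064 + 28 = 1092, a day that the interval rule places in 'After year 4'. SAP Table 2 keeps the Week 208 visit whole, with a window of LTE Study Days 1079 to 1106. It lists that visit's scheduled day as 1092, although its own formula gives 1092 + 1 = 1093; the two should be reconciled.

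**8. Would moving the cuts suffice?** With Years 2 to 4 ending at LTE Study Days 378, 742 and 1106 (that is, first dose + 377, + 741 and + 1105), and onset at sampling without dropout, the simulated rates are 0.95 / 0.99 / 0.99 / 0.00. With onset uniformly 7 to 14 days after sampling, 84 of the 120 scatter-and-lag combinations fall before the moved cut and 36 (30%) after it. The remainder runs from 1106 to 1148, or 43 days, so it shows 0.30 × 364/43 = 2.5 times truth. Moving the cuts alone therefore works only if onset is dated at sampling.

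**The case against.** The strongest reply is that the consequence is limited. The primary assessment compares Randomised Anifrolumab 300 mg with Randomised Placebo, overall AESI rates do not depend on the cuts, and both groups shift in the same direction. The SAP also plans a Kaplan-Meier plot for each AESI category, where clustering at test dates would be visible. All of this stands, and it confines the point to the by-interval table.

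Several stronger readings are tempting but not supported:

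- A reader might infer a steady rise of about 7-fold. That ratio divides 'After year 4' by Year 2 when Year 2 is itself depressed (3.4/0.49 = 6.9). Years 3 and 4 are flat, so the pattern is a single jump in a short last interval. The low Year 2 also disappears under later onset dating.
- A reader might infer that every screen-detected event moves to the next interval. With onset at sampling and symmetric scatter, 7/15 (47%) of tests stay in the correct year.
- A reader might extend the point to malignancy or to all AESIs. The closing Pap smear is due within three months of the last dose and follow-up smears may follow local guidelines, so they are not tied to the cut day. Nothing can be quantified there.
- A reader might take the vital-signs rule as proof that the problem was recognised. It changes only the end of Year 4, keeps the other cuts, and comes with no stated reason.

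**Conclusion.** The point holds for TB conversions in the by-interval AESI table. Followed as written, SAP 3.1.1 gives an inflated TB rate in 'After year 4' even when the true conversion rate is constant. The inflation is about 3.3 to 3.5 times truth with onset at sampling and symmetric visit scatter, and about 6.3 to 6.4 times truth with visits on the nominal day or onset dated 7 or more days later. Later dating is plausible, because Protocol 6.5.5 defines latent TB by a repeat positive test.

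Year 2 is about half of truth if onset is dated at sampling with scattered visits, and lower still if visits fall exactly on the nominal day. With later dating it is not depressed.

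The coincidence of cuts and test days, and the length of the last interval, come from the documents. Visit scatter, onset lag, perfect detection and the conversion rate are assumptions; the ratios barely depend on the conversion rate. The harm is to reading TB risk over time. Other screen-detected AESIs may be affected, but this is not quantified.

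**What to change.** In SAP 3.1.1, for the by-interval AE, AESI and SAE tables:

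1. End Years 2, 3 and 4 at the upper limit of the SAP's own windows for the annual visits. Table 2 starts with an upper limit of Day 42 for Week 56 and adds 28 days per visit: 42 + 12 × 28 = 378, 42 + 25 × 28 = 742 and 42 + 38 × 28 = 1106. Cut person-time at the same days.
2. Assign each test-detected latent TB AESI to the interval closed by the scheduled test that triggered it, using the sample date. The LTE Day 1 sample goes to Year 1. This rule is essential, because moving the cuts alone fails if onset is dated at the result or retest.
3. Report the remaining time as a separate post-treatment follow-up row. It stays in the table, so genuine late events remain visible, but it is not read as part of the exposure trend.

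**Cost.** SAP wording, three constants and one assignment rule in programming. Year 2 becomes 378 days instead of 364, which the person-time denominator absorbs. Year 4 takes in about two weeks (first dose + 1093 to + 1105) that the SAP elsewhere calls follow-up; a footnote should say so. The follow-up row will show few or no routine-test conversions by construction and should carry the same note.

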### **1.3 Number of subjects**

No formal comparisons are planned in this study; point estimates and confidence intervals (CIs) will be presented for each treatment group separately. The sample size is not based on statistical considerations, but is defined as all subjects who completed the treatment period in

the Phase 3 feeder Studies D3461C00004 or D3461C00005 (through Week 52) and met all study eligibility criteria. Assuming annual dropout rates of 30%, 30%, and 20% following placebo, anifrolumab 150 mg, and anifrolumab 300 mg, and that 90% of the subjects completing studies D3461C00004 or D3461C00005 enter the LTE, follow-up times of approximately 893, 517, and 1343 subject years for the “Randomised Anifrolumab 300 mg,” “Randomised Placebo,” and “All Anifrolumab” treatment groups are expected. Given this exposure, the 95% CIs for an AESI for which the observed incidence rate is 10 events in 1000 subject years will be 5.21 to 19.21 for “Randomised Anifrolumab 300 mg,” and 4.24 to 23.57 for “Randomised Placebo.” For an AESI for which the observed incidence rate is 1 event in 1000 subject years, the 95% CI will be 0.18 to 5.42 for “All Anifrolumab” (0.13 to 7.95 for “Randomised Anifrolumab 300 mg”), and 0.07 to 15.25 for “Randomised Placebo,” using the Rothman-Greenland Method ([Rothman and Greenland, 1998](#)).

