If an AE has a missing onset date, then unless the stop date of the AE indicates otherwise, it will be assigned to the “Year 1” time interval. Similarly, if an AE has a partial onset date, then unless the partial onset date or the stop date indicates otherwise, it will be assigned to the earliest time interval given the available date information. If the missing or partial start date does not allow an assignment of the event as during the Phase 3 feeder studies or the LTE study, the AE will be assigned to “Year 1” if documented in one of the Phase 3 feeder studies or to “Year 2” if documented in the LTE.

The event rate per 100 subject years is defined as the number of subjects with an event divided by the sum of exposure time in days in the respective time period for all subjects in the analysis set multiplied by 365.25 days/year multiplied by 100. The exposure in a time period for each subject will be calculated as end of period – start of period + 1 (e.g., as the earlier of either (date of last dose of investigational product + 84 days, or date of study discontinuation) - date of first dose of investigational product + 1 day for the summary of all AEs during treatment and follow-up; for AEs during treatment, the same definition will apply, with the exception of last dose of investigational product + 28 days will be used). For analyses based on LTE data only (e.g. AE rates for subjects switching from Placebo to 300 mg anifrolumab in the “All Anifrolumab” treatment group), the first administration of investigational product during the LTE will be considered as the start of the overall period. For analyses based on feeder study data only (e.g. AE rates for subjects switching from Placebo to 300 mg anifrolumab in the “All Randomised Placebo” treatment group), the end of the overall period will be defined as the first administration of investigational product in the LTE -1 day. If a subject discontinued during a period or had the last follow-up visit earlier than expected, the date of study discontinuation/end of study will be used as end of the respective period.

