### **4.2.1 Analysis of the primary variables (safety variables)**

If not stated otherwise, safety variables will be summarised by combined treatment group for the full analysis set.

The primary assessment will be the comparison between the treatment groups “Randomised Anifrolumab 300 mg” and “Randomised Placebo”. The “All Anifrolumab” treatment group will be used to assess rare events.

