#### 4.2.1.1 Adverse events

Even not stated explicitly, all summaries described below will be based on AEs during treatment and follow-up.

An overall summary of subjects with at least 1 AE in the following categories will be presented as event rates per 100 subject years. This summary will also be presented for the additional supportive treatment groups placebo feeder + anifrolumab 300 mg LTE, and anifrolumab 150 mg feeder + anifrolumab 300 mg LTE. This summary will also be presented for the LTE Study only.

- Any AE
- Any AE with outcome = death
- Any SAE (including events with outcome = death)
- Any AE leading to discontinuation of investigational product
- Any AE related to investigational product
- Any AE of severe intensity
- Any AESI
  - Any AESI of non-opportunistic serious infections
  - Any AESI of opportunistic infections
  - Any AESI of anaphylaxis
  - Any AESI of malignancy
  - Any AESI of herpes zoster
  - Any AESI of tuberculosis
  - Any AESI of influenza
  - Any AESI of vasculitis (non SLE)
  - Any AESI of major acute cardiovascular events
- Any other significant AE

The overall summary above will be repeated for the sub-periods prior to the COVID-19 pandemic (events prior to 11-Mar-2020) and during the COVID-19 pandemic (events on or after the COVID-19 pandemic; only subjects remaining in the study on 11-Mar-2020 will be included). These summaries will be presented for the LTE study only. Alternative event rates and event rates will be computed. As sensitivity analysis the overall summary will be repeated including subjects excluded from analysis (see Section 4.1.1).

An overall summary of subjects with at least one COVID-19 related AE in the following categories will be presented as alternative event rates per 100 subject years. This summary will be presented for the LTE Study only. Only subjects remaining in the study on 11-Mar-2020 will be included.

- Any COVID-19 related AE

- Any COVID-19 related AE with outcome = death
- Any COVID-19 related SAE (including events with outcome = death)
- Any COVID-19 related AE leading to discontinuation of investigational product
- Any COVID-19 related AE related to investigational product
- Any COVID-19 related AE of severe intensity

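### The SAP's main event rate counts each subject once but keeps exposure after the first event; it is not the protocol's rate, and the output list gives the SAE total no whole-period first-event rate

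*SAP*

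**What the plan says.** Rates of AESIs and SAEs are the only primary outcome measure. Protocol 8.5.1 summarises them as "incidence rates (ie, number of events divided by person-time at risk".

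SAP 3.1.1 defines two rates.
- **Event rate:** "event rate per 100 subject years is defined as the number of subjects with an event divided by the sum of exposure time", scaled to 100 years. For events during treatment and follow-up, exposure runs to the last dose plus 84 days or to study discontinuation, whichever is earlier.
- **Alternative event rate:** the same numerator over time at risk, which ends at the first event, death, withdrawal of consent or end of period. It is an additional analysis whose scope names AESIs, SAEs and COVID-19 related AEs.

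SAP 4.2.1.1 assigns the rates to outputs.
- The overall summary, which includes any AESI and any SAE, "will be presented as event rates per 100 subject years".
- The rate tables with 95% CIs include any AESI twice over the whole period, once with each rate.
- They include "Any SAE (including events with outcome = death) (during treatment and during follow-up separately", with the event rate, and "Any SAE (including events with outcome = death) by time interval for the first onset of event", with the alternative rate.
- Both rates are promised for the repeats of the overall summary before and during the pandemic, in LTE data only.
- Herpes zoster gets the alternative rate overall and by interval, including its serious subcategory.

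SAP 1.3 plans no formal comparisons and says "point estimates and confidence intervals (CIs) will be presented for each treatment group separately". SAP 4.2.1 adds: "The primary assessment will be the comparison between the treatment groups" Randomised Anifrolumab 300 mg and Randomised Placebo.

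**The concern.** If the protocol means all events, the SAP's event rate drops repeat events from the numerator. If it means first events, the SAP keeps time in the denominator when the subject can no longer have a first event. Neither reading yields the SAP's quantity.

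The hybrid rate falls further below the first-event rate the longer subjects are followed. The two primary groups are followed for different lengths of time by design: placebo subjects who switch to anifrolumab stop contributing to Randomised Placebo at the switch (SAP 2.1.6), and assumed annual dropout is 30% on placebo against 20% on anifrolumab 300 mg (SAP 1.3). The main comparison can therefore move even when the hazards are equal. With equal hazards, or a higher hazard on anifrolumab, the shift makes an excess risk look smaller.

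**Working it through.** **Inputs from SAP 1.3 and 1.2:** annual dropout 20% (anifrolumab 300 mg) and 30% (placebo); 90% of completers enter the LTE; placebo entrants re-randomised 1:1; one feeder year plus three LTE years. **Assumed:** 360 subjects per arm, dropout uniform within each year, constant hazard.

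**Step 1: reproduce the planned follow-up.**
- Anifrolumab: 0.9 + (0.8 × 0.9) × 0.9 × (1 + 0.8 + 0.64) = 0.9 + 1.581 = 2.481 years. × 360 = 893.2 subject-years (SAP: 893).
- Placebo: 0.85 + (0.7 × 0.9 × 0.5) × 0.85 × (1 + 0.7 + 0.49) = 0.85 + 0.586 = 1.436 years. × 360 = 517.1 subject-years (SAP: 517).

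The factor 0.7 × 0.9 × 0.5 = 0.315 is the share of placebo subjects who leave the group at the switch, and equally the share who continue on placebo. With dropout spread exponentially within years, the implied sizes are about 361 and 364 and the ratios below do not change.

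**Step 2: what each rate estimates.** With hazard λ and follow-up T:
- event rate = E[1 − exp(−λT)] / E[T];
- alternative rate = E[1 − exp(−λT)] / E[min(T, first-event time)] = λ.

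At λ = 10 per 100 subject-years, the expected subjects with an event are 76.1 and 46.1. The event rate is 76.1/893.2 = 8.52 and 46.1/517.1 = 8.92 per 100, a shortfall of 14.8% and 10.8%. The ratio is 0.955, although the true ratio is 1.

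**Step 3: shift in the comparison under equal hazards.** The last column is |ln ratio| divided by 1.96 × √(1/a + 1/b), where a and b are the expected subjects with an event.

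| True rate per 100 SY | Event rate, anifrolumab / placebo | Ratio | Subjects a / b | Shift as share of CI half-width |
|---|---|---|---|---|
| 1 | 0.98 / 0.99 | 0.995 | 8.8 / 5.1 | 0.4% |
| 5 | 4.61 / 4.72 | 0.977 | 41.2 / 24.4 | 5% |
| 10 | 8.52 / 8.92 | 0.955 | 76.1 / 46.1 | 13% |
| 15 | 11.86 / 12.69 | 0.934 | 105.9 / 65.6 | 22% |
| 20 | 14.71 / 16.08 | 0.915 | 131.4 / 83.2 | 33% |

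The plan's own planning rates, 1 and 10 per 1000, are 0.1 and 1 on this scale; at 0.1 the ratio is 0.9995. The range 5 to 20 is assumed for composites.

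**Step 4: sensitivity.**
- A true ratio of 2.0 shows as 1.81 (10 against 5 per 100) or 1.65 (20 against 10).
- With 20% dropout in both arms, the ratio at 10 is still 0.969, because the switch alone unbalances follow-up.
- The direction reverses once the placebo hazard is about 1.4 to 1.5 times the anifrolumab hazard.
- In LTE-only tables the ratio at 10 is 0.991.

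**Step 5: per-group intervals, if the first-event rate is the target.** In simulated trials (360 per arm, exact Poisson 95% CI), the interval on the event rate covers the true first-event rate about 95% of the time or more at 1 and 5 per 100. At 10 it covers about 77% (anifrolumab) and 92% (placebo); at 15, about 26% and 77%. The alternative rate stays at about 95% or above.

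**Step 6: limit of the alternative rate.** If hazards vary between subjects (gamma frailty, variance 1, assumed, at 15 per 100), the whole-period ratio is 0.949 with the alternative rate and 0.897 with the event rate. Within yearly intervals the alternative-rate ratio is about 0.999.

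**The case against.** Much is already planned. The SAP commits in general terms to first-event rates for SAEs, lists them by interval, and gives AESIs the whole-period version plus Kaplan-Meier plots by category. The intervals break at LTE entry, where the switch occurs, so the by-interval SAE rates already remove most of the imbalance. The table shells are a separate document and may contain the missing output. No between-group ratio is a listed output, and even at 10 per 100 subject-years the shift is a small part of the statistical uncertainty. All of this stands. It limits the point to a gap in the output list and to how common composites are read.

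Four stronger readings are tempting but unsupported.
- **No SAE gets a whole-period first-event rate.** Serious non-opportunistic infections are AESIs by definition (Protocol 6.5.1.1) and get it there, as does serious herpes zoster. The gap concerns the SAE total and its breakdown by system organ class and preferred term.
- **The plan systematically favours anifrolumab.** The direction depends on the unknown hazards and can reverse.
- **The confidence intervals are invalid.** The coverage shortfall arises only if the first-event rate is the target and only at assumed rates. The SAP does not say that its event rate estimates that quantity.
- **The departure was left unrecorded.** The visible part of SAP Section 6 does not mention it, but part of that section is redacted.

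Conversely, the sentence promising both rates does not close the gap: in context it covers the LTE-only pandemic sub-periods.

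**Conclusion.** The definitional mismatch is clear from the text and needs no assumption: the SAP's event rate is not the protocol's rate on either reading. The gap in the output list is also clear in the documents available.

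The numerical consequence is negligible for rare AESIs and modest for common composites: a ratio of 0.977 to 0.915 over an assumed 5 to 20 per 100 subject-years when the true ratio is 1. This rests on 360 per arm, constant hazards and the plan's dropout assumptions. The documents give no expected rate for any SAE or any AESI. The point is worth correcting because it touches half of the primary outcome and the SAP already defines the remedy.

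A separate, secondary mismatch concerns flares. Protocol 8.5.1 specifies "number of flares divided by person-time at risk", while SAP 3.1.5 counts subjects with a flare over full exposure. Flares are not a primary variable, and the effect is not quantified here.

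**What to change.** 1. In SAP 4.2.1.1, add any SAE with alternative event rates and 95% CIs over the whole combined feeder and LTE period, matching the existing AESI line.
2. In the overall summary, show both rates for any AESI and any SAE, as already planned for the pandemic sub-periods. Label the event rate 'subjects with an event per total exposure'. Showing both avoids unlabelled mixed denominators in one table.
3. Base the reading of Randomised Anifrolumab 300 mg against Randomised Placebo, for AESIs and SAEs, on the alternative rate together with the planned by-interval rates, since the whole-period rate alone is exact only under constant hazards.
4. State whether Protocol 8.5.1 means first or all events, and record the rate definition in SAP Section 6 if the redacted text does not.
5. Separately, align the flare rate in SAP 3.1.5 with Protocol 8.5.1, or record the change.

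The cost is SAP wording, one added SAE output, extra columns in one summary and a small programming change to a rate already defined. If the flare rate is aligned, flares must also be counted as events. No new data are needed. First-event rates will be higher than the event rates in both groups, visibly so for common composites. The other AE tables can stay.
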